7 CHANGES IN THE PLANNED ANALYSES

Not applicable.

8 DEFINITIONS AND CONVENTIONS FOR DATA HANDLING

Study Day 1

Study Day 1 is defined as the day of the first dose of study drug administered.

Baseline

Baseline is defined as a Day 1 pre-dose, the last observation before the start of drug, if the Day 1 pre-dose is missing.

By-visit analyses

All by-visit analyses will be performed using assessments at corresponding scheduled visits recorded in the eCRF. For shift tables, all post-baseline assessments including those at scheduled and unscheduled visits will be used.

Incomplete dates

For incomplete dates involving efficacy and safety data, see [Section 5.3.4](#) for data handlings.

Limit of Quantification (BLQ) in pharmacokinetics analyses

When calculating the mean or median value for the concentrations at a given time point, the BLQ values will be assigned as zero. If the proportion of values reported as BLQ is more than 50%, no summary statistics should be represented at that time point, and the value will be treated as missing in mean or median concentration profiles.

More specific details, if any, are given with the discussion of analyses for each endpoint. Details on the way that BLQ values will be replaced will be described in a separate plan detailing the analyses.

9 PROGRAMMING SPECIFICATIONS

The rules for programming derivations and dataset specifications will be provided in separate documents.

10 STATISTICAL SOFTWARE

Statistical programming and analyses will be performed using SAS® (SAS Institute, Inc., Cary, NC, USA), version 9 or higher, and/or other validated statistical software as required.

11 MOCK TABLES, LISTINGS AND GRAPHS (TLGS)

The study TLG shells will be provided in a separate document, which will show the content and format of all tables, listings, and graphs in detail.

13 APPENDICES

13.1 Immune-Related Response Evaluation Criteria In Solid Tumors (irRECIST)

Investigators should follow the guidelines provided here which are an adaptation of RECIST 1.1 and immune-related response criteria (irRC). The following guide represents a summary of irRECIST and is meant to help investigators in providing more objective and reproducible immune therapy related tumor response assessments in solid tumors.

The key changes for irRECIST are:

- In contrast to RECIST 1.1, irRECIST allows the site to select up to ten (10) target lesions at baseline, five (5) per organ, if clinically relevant via CT/MRI scans or by electronic calipers for skin lesions. The ability to continue treatment, if clinically stable, until repeat imaging scans \geq 4 weeks later (in most cases at the next scanning time point 6 weeks later) to confirm Progressive Disease (PD)

irRECIST Lexicon	
1. Baseline Assessments	
Measurable (Target) lesions	
Measurable lesions must be accurately measured in at least one dimension with a minimum size of:
 
 • 10 mm in the longest diameter (LDi) by CT or MRI scan (or no less than double the slice thickness) for non-nodal lesions and \geq15 mm in short axis (SDi) for nodal lesions • 10 mm in LDi for clinical lesions (must be measured using electronic calipers) • Identify up to 10 lesions, not more than 5 from one organ system. Lymph nodes are considered one organ system • Likely to be reproducible across all time points • Representative of tumor burden • May include lesions in previously irradiated areas ONLY if there is demonstrated progression in that lesion after irradiation • Sum of diameters (SOD) of all target lesions including nodal and non-nodal are reported as baseline SOD which is used for assessing tumor response at follow-up time points
Bone lesions	Regardless of the imaging modality, blastic bone lesions will not be selected as target lesions. Lytic or mixed lytic-blastic lesions with a measurable soft tissue component \geq 10 mm can be selected as target lesions.

Cystic and Necrotic Lesions as Target Lesions	Lesions that are partially cystic or necrotic can be selected as target lesions. The longest diameter of such a lesion will be added to the SOD of all target lesions at baseline. If other lesions with a nonliquid/nonnecrotic component are present, those should be preferred.
Lesions with Prior Local Treatment	During target lesion selection the radiologist will consider information on the anatomical sites of previous intervention (e.g. previous irradiation, RF-ablation, TACE, surgery, etc.). Lesions undergoing prior intervention will not be selected as target lesions unless there has been a demonstration of progression in the lesion.
Nonmeasurable (Non-Target) lesions	
Non-target lesions will include:
 
 • Measurable lesions not selected as target lesions. There is no limit to the number of non-target lesions that can be recorded at baseline • Other types of lesions that are confidently felt to represent neoplastic tissue, but are difficult to measure in a reproducible manner. These include bone metastases, leptomeningeal metastases, malignant ascites, pleural or pericardial effusions, ascites, inflammatory breast disease, lymphangitis cutis/pulmonis, cystic lesions, ill-defined abdominal masses, skin lesions, etc. • Multiple non-target lesions from the same organ may be captured as a single item on the eCRF (e.g. multiple liver metastases) 
Non-target lesions should be reported as present at baseline

SOD _{baseline}	Sum of diameters at baseline = LDi of all non-nodal + SDi of all nodal target lesions
2. Time Point Assessments After Baseline	
Target lesion measurements	
Locate image that optimizes the LDi of the non-nodal target lesion or short axis of target node(s). There is no need to go to an identical slice from baseline.
 
Measure the respective LDi and SDi for all target lesions and calculate time point SOD (SOD_{timepoint}).
 
Special consideration for target lesions:
 
 • If target lesion is too small to measure, a default value of 5mm should be entered on eCRF. • If target lesion is 5-10mm, actual diameter should be entered in the eCRF • If target lesion splits into 2 or more lesion then the LDi of split lesions will be added and entered in place of that lesion • If two target lesion merged to form one lesion than LDi of one should be entered as "0mm" while the other lesion should have the diameter of the merged lesion

Nontarget Lesion Assessment	Nontarget lesions are evaluated qualitatively as present, absent, not evaluable (NE) or unequivocal progression. The response of nontarget lesions primarily contributes to the overall response assessments of CR. Nontarget lesions do not affect PR and SD assessments. Only a massive and unequivocal worsening of nontarget lesions alone, even in the presence of stable disease or a partial response in the target lesion is indicative of PD. CR is not possible unless all non-target lesions are absent.
Definition of New lesion	Any lesion which was not recorded at baseline. There is no minimum size criteria to identify a new lesion and clinical judgment must be used by the PI. 
 • May include a lesion in an anatomical location that was not scanned at baseline (i.e. brain) • Should be unequivocal and not due to differences in scanning technique • If equivocal, should be assessed at next timepoint; if present, PD is the date the lesion was first seen (not the date confirmed)
3. irRECIST Overall Tumor Assessment	
CR	
 • Complete disappearance of all measurable and nonmeasurable lesions (from baseline) and there are no unequivocal new lesions (unconfirmed CR). • Lymph nodes must decrease to < 10 mm in short axis. • Confirmation of response is required ≥ 4 weeks later, preferably at next time point, to be considered a confirmed CR.
PR	
 • If the SOD_{timepoint} of TLs decreases by $\geq 30\%$ compared to SOD_{baseline} and there are no unequivocal new lesions, and no progression of nontarget disease, it is an PR (unconfirmed). • Confirmation is required ≥ 4 weeks later, preferably at next time point, to be considered a confirmed PR.
SD	
Failure to meet criteria for CR or PR in the absence of PD.
 
 • If the sum of the TLs and the status of the nontarget lesions do not reach the criteria to meet PR or PD (increase $\geq 20\%$ and at least 5 mm absolute increase in SOD compared to nadir[†]) the response is SD. • SD = neither 30% decrease compared to SOD_{baseline} or 20% increase and at least 5 mm absolute change compared to nadir. • †SOD_{nadir}: Lowest measure SOD of TLs at any time point from baseline onward.
PD	Minimum 20% increase and a minimum 5 mm absolute increase in SOD compared to nadir, or PD for nontarget lesion(s) or unequivocal new lesion(s).

	
 Confirmation of progression is recommended at a minimum of 4 weeks after the first PD assessment (preferably at next tumor assessment time point). 
The decision to continue study treatment after the first evidence of PD is at the Investigator's discretion based on the clinical status of the subject as described in table below
																									
	
  
 	Clinically Stable	Clinically Unstable	
 
 	Imaging	Treatment	Imaging	Treatment	
   
 1st radiologic evidence of PD	Repeat imaging at \geq 4 weeks (next TA time point) to confirm PD	May continue study treatment at the Investigator's discretion while awaiting confirmatory scans	Repeat imaging at \geq 4 weeks to confirm PD per physician discretion only	Discontinue treatment	
 
 Subsequent scan confirms PD	No additional imaging required	Discontinue treatment	No additional imaging required	N/A	
 
 Subsequent scan shows SD, PR or CR	Continue regularly scheduled imaging assessments	Continue study treatment at the Investigator's discretion	Continue regularly scheduled imaging assessments	May restart study treatment if condition has improved and/or clinically stable per Investigator's discretion	
  
		Clinically Stable		Clinically Unstable			Imaging	Treatment	Imaging	Treatment	1 st radiologic evidence of PD	Repeat imaging at \geq 4 weeks (next TA time point) to confirm PD	May continue study treatment at the Investigator's discretion while awaiting confirmatory scans	Repeat imaging at \geq 4 weeks to confirm PD per physician discretion only	Discontinue treatment	Subsequent scan confirms PD	No additional imaging required	Discontinue treatment	No additional imaging required	N/A	Subsequent scan shows SD, PR or CR	Continue regularly scheduled imaging assessments	Continue study treatment at the Investigator's discretion	Continue regularly scheduled imaging assessments	May restart study treatment if condition has improved and/or clinically stable per Investigator's discretion
	Clinically Stable		Clinically Unstable																							
	Imaging	Treatment	Imaging	Treatment																						
1 st radiologic evidence of PD	Repeat imaging at \geq 4 weeks (next TA time point) to confirm PD	May continue study treatment at the Investigator's discretion while awaiting confirmatory scans	Repeat imaging at \geq 4 weeks to confirm PD per physician discretion only	Discontinue treatment																						
Subsequent scan confirms PD	No additional imaging required	Discontinue treatment	No additional imaging required	N/A																						
Subsequent scan shows SD, PR or CR	Continue regularly scheduled imaging assessments	Continue study treatment at the Investigator's discretion	Continue regularly scheduled imaging assessments	May restart study treatment if condition has improved and/or clinically stable per Investigator's discretion																						
	Subjects may continue receiving study treatment while waiting for confirmation of PD if they are clinically stable as defined by the following criteria:																									

	
 • Absence of signs and symptoms (including worsening of laboratory values) indicating disease progression • No decline in ECOG performance status • Absence of rapid progression of disease • Absence of progressive tumor at critical anatomical sites (e.g., cord compression) requiring urgent alternative medical intervention 
If PD is confirmed and the subject is experiencing extraordinary clinical benefit, site must contact Sponsor to discuss continuing treatment

NE	Used in exceptional cases where insufficient data exists due to poor quality of scans or missed scans or procedure

Derivation of irRECIST overall responses			
Measurable response	Nonmeasureable response		
Target Lesions (% change in SOD)*	Non-Target Lesions Status	New Lesions Status	Overall Response (irRECIST)
↓100	Absent	Absent	CR [¥]
↓100	Present/NE	Absent	PR [¥]
↓≥30	Present/Absent/NE	Absent	PR [¥]
↓<30 to <20↑	Present/Absent/NE	Absent	SD
↓100 ↓≥30 ↓<30 to <20↑ NE	Present/Absent/NE	Present	PD [¥]
↓100 ↓≥30 ↓<30 to <20↑ NE	Unequivocal progression	Any	PD [¥]
↑≥20 from nadir	Any	Any	PD [¥]
NE	Present/Absent/NE	Absent	NE [¥]

* Decreases assessed relative to baseline, including measureable lesions only.

[†] Assuming response (CR and PR) and progression (PD) are confirmed by a second, consecutive assessment at least 4 week apart.

13.2 Dose-Limiting Toxicities

A Dose-limiting toxicity (DLT) is defined as any of the following as judged by the investigator.

- Any of the hematological or nonhematological toxicities noted in the table below considered to be at least possibly related to lenvatinib and/or pembrolizumab occurring during Cycle 1.
- Failure to administer $\geq 75\%$ of the planned dosage of lenvatinib as a result of treatment-related toxicity during Cycle 1.
- Subjects who discontinue treatment due to treatment-related toxicity.
- Greater than 2 week delay in starting Cycle 2 because of a treatment-related toxicity, even if the toxicity does not meet DLT criteria.

Dose Limiting Toxicities	
Toxicity Category	Toxicity CTCAE Grade
Hematologic	Grade 4 neutropenia for ≥ 7 days
	Grade 3 or Grade 4 febrile neutropenia ^a
	Thrombocytopenia $<25,000/\text{mm}^3$ associated with bleeding and/or that requires platelet transfusion
Other nonhematologic toxicity	Any other Grade 4 or a Grade 5 toxicity Grade 3 toxicities lasting >3 days excluding: Nausea, vomiting, and diarrhea controlled by medical intervention within 72 hours. Grade 3 rash in the absence of desquamation, no mucosal involvement, does not require steroids, and resolves to Grade 1 by the next scheduled dose of pembrolizumab.
	Grade 3 hypertension not able to be controlled by medication
	Grade 3 or above gastrointestinal perforation
	Grade 3 or above wound dehiscence requiring medical or surgical intervention
	Any grade thromboembolic event

	Any Grade 3 nonhematologic laboratory value if: Medical intervention is required to treat the subject, or the abnormality leads to hospitalization
ANC = absolute neutrophil count, CTCAE = Common Terminology Criteria for Adverse Events v4.03.	
a. Febrile neutropenia Grade 3 or Grade 4: Grade 3 is defined as ANC <1000/mm³ with a single temperature of >38.3 °C (101 °F) or a sustained temperature of ≥38 °C (100.4 °F) for more than one hour. Grade 4 is defined as ANC <1000/mm³ with a single temperature of >38.3 °C (101 °F) or a sustained temperature of ≥38 °C (100.4 °F) for more than one hour, with life-threatening consequences and urgent intervention indicated

Only toxicities with a clear alternative explanation (eg, due to disease progression) or transient (≤ 72 hours) abnormal laboratory values without associated clinically significant signs or symptoms based on investigator determination can be deemed a non-DLT.

All subjects enrolled in Phase 1b will be assessed for DLTs during the DLT assessment window of Cycle 1 (Treatment Phase). Subjects who discontinue study treatment prior to completing the Treatment Phase for any reason other than DLT will be replaced. Once they complete the Treatment Phase, each subject still receiving study treatment will transition into the Extension Phase. Tumor assessments will continue during the Extension Phase.

13.3 Common Terminology Criteria For Adverse Events (CTCAE) V4.03

The Common Terminology Criteria for Adverse Events ([CTCAE v4.03, published 14 June 2010](#)) provides descriptive terminology to be used for adverse event reporting in clinical trials. A brief definition is provided to clarify the meaning of each AE term. To increase the accuracy of AE reporting, all adverse event terms in CTCAE v4.03 have been correlated with single-concept Medical Dictionary for Regulatory Activities (MedDRA) terms.

The Common Terminology Criteria for Adverse Events v4.03 grading refers to the severity of the AE. The Common Terminology Criteria for Adverse Events grades 1 through 5, with unique clinical descriptions of severity for each AE, are based on this general guideline:

Grade	CTCAE Status
-------	--------------

1	Mild: asymptomatic or mild symptoms; clinical or diagnostic observations only; intervention not indicated
2	Moderate: minimal, local, or noninvasive intervention indicated; limiting age-appropriate instrumental activities of daily living (ADL) ^a
3	Severe or medically significant but not immediately life-threatening: hospitalization or prolongation of hospitalization indicated; disabling, limiting self-care ADL ^b
4	Life-threatening consequences: urgent intervention indicated
5	Death related to adverse event

ADL = activities of daily living, CTCAE = Common Terminology Criteria for Adverse Events.

a: Instrumental ADL refers to preparing meals, shopping for groceries or clothes, using the telephone, managing money, etc.

b: Self-care ADL refers to bathing, dressing and undressing, feeding self, using the toilet, taking medications, and not bedridden.

Adapted from the Cancer Therapy Evaluation Program, NCI. CTCAE v4.03

For further details regarding MedDRA, refer to the MedDRA website at:

<http://www.meddramsso.com>

13.4 New York Heart Association (NYHA) Cardiac Disease Classification

The New York Heart Association Cardiac Disease Classification provides a functional and therapeutic classification for the prescription of physical activity for cardiac subjects. Based on NYHA definitions, subjects are to be classified as follows:

Class	NYHA Status
Class I:	Subjects with no limitation of activities; they suffer no symptoms from ordinary activities.
Class II:	Subjects with slight, mild limitation of activity; they are comfortable with rest or with mild exertion.
Class III:	Subjects with marked limitation of activity; they are comfortable only at rest.
Class IV:	Subjects who should be at complete rest, confined to bed or chair; any physical activity brings on discomfort and symptoms occur at rest.

NYHA = New York Heart Association.

Adapted from The Criteria Committee of the New York Heart Association. Nomenclature and criteria for diagnosis of diseases of the heart and great vessels. 9th ed. New York: Little Brown; 1994. p.253-6.

13.5 Summary of primary and secondary Efficacy Analyses

Based on investigator assessments per irRECIST and mRECIST 1.1 for all 6 tumor cohorts, the following will be included in the efficacy analysis on the full analysis set or tumor specific analysis sets.

Efficacy Variable	Statistical Method
ORR(Week 24)	Number (percent) of subjects (with PR + CR) at Week 24 and its exact 95% CI using method of Clopper-Pearson. (Only for irRECIST)
ORR	Number (percent) of subjects (with PR + CR) and its exact 95% CI using method of Clopper-Pearson.
PFS	Kaplan-Meier method: Median PFS, and progression-free survival rate at 3, 6, 9, and 12 months will be presented with 2-sided 95% CIs. Kaplan-Meier plot will also be provided.
OS*	Kaplan-Meier method: Median OS, and survival rates at 12, 18, and 24 months will be presented with 2-sided 95% CIs. Kaplan-Meier plot will also be provided.
DCR	Number (percent) of subjects (with CR + PR + stable disease [SD] \geq 5 weeks) and its exact 95% CI using method of Clopper-Pearson.
CBR	Number (percent) of subjects (with CR, PR + durable SD \geq 23 weeks) and its exact 95% CI using method of Clopper-Pearson.
DOR	Kaplan-Meier method: Median DOR with 2-sided 95% CIs will be presented.

* The OS endpoint is independent from tumor assessment criteria.

Based on independent imaging review per irRECIST, mRECIST 1.1, RECIST 1.1 for EC and RCC cohorts, the following will be included in efficacy analyses on the Endometrial Carcinoma Analysis Set and Renal Cell Carcinoma Analysis Set.

Efficacy Variable	Statistical Method
ORR _(Week 24)	Number (percent) of subjects (with PR + CR) at Week 24 and its exact 95% CI using method of Clopper-Pearson. (Only for irRECIST)
ORR	Number (percent) of subjects (with PR + CR) and its exact 95% CI using method of Clopper-Pearson.
PFS	Kaplan-Meier method: Median PFS, and progression-free survival rate at 3, 6, 9, and 12 months will be presented with 2-sided 95% CIs. Kaplan-Meier plot will also be provided.
DCR	Number (percent) of subjects (with CR + PR + stable disease [SD] \geq 5 weeks) and its exact 95% CI using method of Clopper-Pearson.
CBR	Number (percent) of subjects (with CR, PR + durable SD \geq 23 weeks) and its exact 95% CI using method of Clopper-Pearson.
DOR	Kaplan-Meier method: Median DOR with 2-sided 95% CIs will be presented.

13.6 Common Terminology Criteria for Adverse Events (CTCAE) for Hematology & Clinical Chemistry

Laboratory Parameter	Common Terminology Criteria for Adverse Events (CTCAE)			
	Grade 1	Grade 2	Grade 3	Grade 4
Hematology				
Hemoglobin	< LLN – 10 g/dL < LLN – 6.2 mmol/L	< 10 – 8 g/dL < 6.2 – 4.9 mmol/L	< 8 – 6.5 g/dL < 4.9 – 4 mmol/L	–
Platelet Count	< LLN – 75,000/mm ³ < LLN – 75 x 10 ⁹ /L	< 75,000 – 50,000/mm ³ < 75 – 50 x 10 ⁹ /L	< 50,000 – 25,000/mm ³ < 50 – 25 x 10 ⁹ /L	< 25,000/mm ³ < 25 x 10 ⁹ /L
Leukocytes (Total WBC)	< LLN – 3,000/mm ³ < LLN – 3 x 10 ⁹ /L	< 3,000 – 2,000/mm ³ < 3 – 2 x 10 ⁹ /L	< 2,000 – 1,000/mm ³ < 2 – 1 x 10 ⁹ /L	< 1,000/mm ³ < 1 x 10 ⁹ /L
Lymphocytes (hypo)	< LLN – 800/mm ³ < LLN – 0.8 x 10 ⁹ /L	< 800 – 500/mm ³ < 0.8 – 0.5 x 10 ⁹ /L	< 500 – 200/mm ³ < 0.5 – 0.2 x 10 ⁹ /L	< 200/mm ³ < 0.2 x 10 ⁹ /L

Laboratory Parameter	Common Terminology Criteria for Adverse Events (CTCAE)			
	Grade 1	Grade 2	Grade 3	Grade 4
Lymphocytes (hyper)	-	> 4,000 – 20,000/mm ³ > 4 – 20 x 10 ⁹ /L	> 20,000/mm ³ > 20 x 10 ⁹ /L	-
Neutrophils	< LLN – 1,500/mm ³ < LLN – 1.5 x 10 ⁹ /L	< 1,500 – 1,000/mm ³ < 1.5 – 1 x 10 ⁹ /L	< 1,000 – 500/mm ³ < 1 – 0.5 x 10 ⁹ /L	< 500/mm ³ < 0.5 x 10 ⁹ /L
	Clinical Chemistry			
Albumin	< LLN – 3 g/dL < LLN – 30 g/L	< 3 – 2 g/dL < 30 – 20 g/L	< 2 g/dL < 20 g/L	
Alkaline Phosphatase	> 1 – ≤ 2.5 x ULN	> 2.5 – ≤ 5 x ULN	> 5 – ≤ 20 x ULN	> 20 x ULN
ALT	> 1 – ≤ 3 x ULN	> 3 – ≤ 5 x ULN	> 5 – ≤ 20 x ULN	> 20 x ULN
Amylase	> 1 – ≤ 1.5 x ULN	> 1.5 – ≤ 2 x ULN	> 2 – ≤ 5 x ULN	> 5 x ULN
AST	> 1 – ≤ 3 x ULN	> 3 – ≤ 5 x ULN	> 5 – ≤ 20 x ULN	> 20 x ULN
Bilirubin, Total	> 1 – ≤ 1.5 x ULN	> 1.5 – ≤ 3 x ULN	> 3 – ≤ 10 x ULN	> 10 x ULN
Calcium (hyper)	> ULN – ≤ 11.5 mg/dL > ULN – ≤ 2.9 mmol/L	> 11.5 – ≤ 12.5 mg/dL > 2.9 – ≤ 3.1 mmol/L	> 12.5 – ≤ 13.5 mg/dL > 3.1 – ≤ 3.4 mmol/L	> 13.5 mg/dL > 3.4 mmol/L
Calcium (hypo)	< LLN – 8 mg/dL < LLN – 2 mmol/L	< 8 – 7 mg/dL < 2 – 1.75 mmol/L	< 7 – 6 mg/dL < 1.75 – 1.5 mmol/L	< 6 mg/dL < 1.5 mmol/L
Cholesterol, Total	> ULN – 300 mg/dL > ULN – 7.75 mmol/L	> 300 – 400 mg/dL > 7.75 – 10.34 mmol/L	> 400 – 500 mg/dL > 10.34 – 12.92 mmol/L	> 500 mg/dL > 12.92 mmol/L
Creatinine	> 1 – ≤ 1.5 x ULN	> 1.5 – ≤ 3 x ULN	> 3 – ≤ 6 x ULN	> 6 x ULN
Glucose (hyper)	> ULN – ≤ 160 mg/dL > ULN – ≤ 8.9 mmol/L	> 160 – ≤ 250 mg/dL > 8.9 – ≤ 13.9 mmol/L	> 250 – ≤ 500 mg/dL > 13.9 – ≤ 27.8 mmol/L	> 500 mg/dL > 27.8 mmol/L

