9.7.1.8.3 LABORATORY VALUES

Laboratory results will be summarized using Système International units, as appropriate. For all quantitative parameters listed in [Section 9.5.1.5.3](#), the actual value and the change from baseline to each postbaseline visit and to the end of treatment will be summarized by visit and treatment using descriptive statistics. Qualitative parameters listed in [Section 9.5.1.5.3](#)

will be summarized using frequencies (number and percentage of subjects), and changes from baseline to each postbaseline visit and to the end of treatment will be reported using shift tables. Percentages will be based on the number of subjects with both nonmissing baseline and relevant postbaseline results.

Laboratory parameters will be categorized according to CTCAE v4.03 grades, and shifts from baseline CTCAE grades to maximum and final postbaseline grades will be assessed. CTCAE v4.03 will be used to identify subjects with treatment-emergent markedly abnormal laboratory values (TEMAV). A more detailed definition of TEMAV will be specified in the SAP. A summary of TEMAVs will be presented by visit and overall and by treatment group.

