5.6.4 Laboratory Values

Laboratory values that are non-missing and reported as ‘below the detectable limit’ of an assay will be replaced by half the detectable limit in the summary tables. Laboratory results will be summarized using the *Système international* (SI) units. Laboratory test results will be assigned a low/normal/high (LNH) classification according to whether the value was below (L), within (N), or above (H) the laboratory parameter’s reference range. Abnormal laboratory values will be identified as those outside the normal range. The abnormal values will be indicated in data listings. Laboratory parameters will also be categorized according to CTCAE v4.03 grades, and shifts from baseline CTCAE grades to worst grades will be assessed.

For quantitative parameters, the actual value and the change from baseline to each post-baseline visit, will be summarized by visit using descriptive statistics if needed. Urinalysis parameters (qualitative) will be listed.

Only laboratory parameters specified in the protocol will be summarized. Other laboratory parameters collected for some individual subjects will be presented in listings.

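### SAP Appendix 13.6 gives no grade to hemoglobin below 6.5 g/dL, so the worst-grade laboratory shift table can understate severe anemia if the table is programmed as printed

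*SAP*

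**What the plan says.** SAP 13.6 grades low hemoglobin in three steps: Grade 1 "< LLN – 10 g/dL < LLN – 6.2 mmol/L", Grade 2 "< 10 – 8 g/dL < 6.2 – 4.9 mmol/L" and Grade 3 "< 8 – 6.5 g/dL < 4.9 – 4 mmol/L". The Grade 4 cell holds a dash.

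The grades feed a planned output. SAP 5.6.4 states: "Laboratory parameters will also be categorized according to CTCAE v4.03 grades, and shifts from baseline CTCAE grades to worst grades will be assessed". Protocol 9.7.1.8.3 plans the same kind of table: "shifts from baseline CTCAE grades to maximum and final postbaseline grades will be assessed". Neither section cites Appendix 13.6; both name CTCAE v4.03. SAP section 9 adds: "The rules for programming derivations and dataset specifications will be provided in separate documents". Those documents are not part of the protocol or SAP.

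**The concern.** A grading table has to place every abnormal result somewhere. This row stops at 6.5 g/dL and has nothing beyond it, so the lowest values, which matter most, are the ones left without a grade. A worst-grade derivation normally takes the maximum over non-missing grades. It would skip the ungraded value and report the subject's next worst result.

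The shift to worst grade is the only graded laboratory summary that SAP 5.6.4 describes. Entry requires hemoglobin of at least 9.0 g/dL (Protocol 9.3.1, criterion 7), so a later value below 6.5 lies more than 9.0 − 6.5 = 2.5 g/dL under the entry limit. A shift table exists to show falls of that kind.

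**Working it through.** The plan gives no figure to reproduce here. The check is whether the printed rows cover all values, and what follows for a worst grade.

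**1. Coverage of the hemoglobin row (SAP 13.6).** Read as printed, 8.0 g/dL is Grade 2, 7.9 is Grade 3 and 6.5 is Grade 3. Values of 6.4, 6.0 and 5.0 g/dL have no grade.

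**2. Both unit systems.** The paired limits give 6.2/10 = 0.62, 4.9/8 = 0.61 and 4/6.5 = 0.62 mmol/L per g/dL. The two scales agree to rounding, so the row closes at the same point in both and a mistyped unit does not explain the gap.

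**3. Comparison with the other rows.** The table shows 17 rows.
- 14 have an open-ended Grade 4 (for example platelets below 25,000/mm³ and ALT above 20 × ULN).
- 2 have no Grade 4 but an open-ended Grade 3: albumin (below 2 g/dL) and high lymphocytes ("> 20,000/mm ³ > 20 x 10 ⁹ /L").
- 1, hemoglobin, has a closed Grade 3 and no Grade 4.

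14 + 2 + 1 = 17. The high-lymphocyte row also prints a dash under Grade 4, so the hemoglobin dash looks deliberate and not like a lost cell. What is missing is the open end on Grade 3.

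**4. Effect on the worst grade.** The series below are illustrative, and a lower limit of normal of 12 g/dL is assumed. The worst grade is the maximum of the non-missing grades.

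| Postbaseline values (g/dL) | Grades as printed | Worst grade as printed | Worst grade if Grade 3 is open-ended |
|---|---|---|---|
| 11, 9.2, 6.2 | 1, 2, none | 2 | 3 |
| 11, 10.5, 6.0 | 1, 1, none | 1 | 3 |
| 13, 6.3 | 0, none | 0 (no abnormal grade) | 3 |
| 11, 7.5, 6.2 | 1, 3, none | 3 | 3 (unchanged) |

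The last line sets the limit of the problem. One other postbaseline value from 6.5 to below 8 g/dL is enough to show Grade 3. Only subjects without such a value are shown wrongly, and always at too mild a grade.

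**The case against.** The strongest reply is that Appendix 13.6 may not be the operative rule. SAP 5.6.4 refers to CTCAE v4.03 in general, and the derivation rules are held elsewhere, so the programs may already grade these values. This stands as a condition on the finding. It does not remove it, because nothing in either document shows that the gap is closed, and the SAP prints a table that cannot grade every result. The table as available also ends at high glucose without a key, so an explanatory footnote cannot be excluded. No footnote marker is visible on the dash.

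The second reply concerns reach, and it also stands. A reader might infer that every subject with a nadir below 6.5 g/dL is misgraded. The documents do not support that. SAP section 8 includes unscheduled results in shift tables. Footnote i of Protocol Tables 8 and 9 calls for repeat tests at least every 7 days while clinically significant hematologic toxicity of Grade 3 or worse persists. Both make a second value in the 6.5 to below 8 band more likely. They do not guarantee one: Protocol 9.4.7 allows transfusion, which can carry a subject past the band between two tests.

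A reader might also infer that severe anemia vanishes from the safety report. It does not. A laboratory abnormality that leads to intervention or to withholding of drug is to be considered an adverse event (Protocol 9.5.1.5.1). Adverse events carry an investigator's CTCAE grade and enter the graded tables of SAP 5.6.3. The low/normal/high classification and the flagged listings of SAP 5.6.4 do not depend on Appendix 13.6.

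The protocol also promises a summary of markedly abnormal values: "A summary of TEMAVs will be presented by visit and overall and by treatment group". The SAP does not contain it. That is a separate matter and adds no weight to the hemoglobin row.

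**Conclusion.** The gap is real and plain on the face of SAP 13.6: hemoglobin below 6.5 g/dL (4 mmol/L) has no grade. The consequence is conditional. It requires that the row be programmed as printed, and it reaches only subjects who fall below 6.5 g/dL with no other postbaseline value from 6.5 to below 8 g/dL. For them, the baseline-to-worst-grade shift shows a milder grade or none.

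The number of such subjects cannot be derived from the documents. A reader might apply an assumed rate of 1% to 2% to the planned total of 120 + 145 + 4 × 20 = 345 in Phase 2 plus 10 to 30 in Phase 1b, that is 355 to 375, and obtain 0.01 × 355 = 3.6 to 0.02 × 375 = 7.5 subjects. The rate has no source in the plan, and the product includes subjects who would still show Grade 3. At most it is a ceiling under that assumption.

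The issue is minor to moderate: confined to graded laboratory summaries, always in the direction of understatement, with no effect on efficacy, dose determination or sample size.

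**What to change.** 1. In SAP 13.6, check the hemoglobin row against the CTCAE v4.03 text that the SAP cites, which the protocol and SAP do not reproduce. Then make the worst category open-ended so that every value below 6.5 g/dL is Grade 3 or higher. With no Grade 4 listed, Grade 3 becomes below 8 g/dL (below 4.9 mmol/L).
2. In SAP 5.6.4, cite Appendix 13.6 so that the rule behind the shift table is explicit.
3. In the programming specifications, add a check that every non-missing result for a graded parameter receives a grade or is classed as normal.

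The cost is one table cell, one cross-reference and one program line. No data collection, efficacy analysis or clinical management rule changes.
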